7.2.4. Reporting Overdose

If a participant takes more than the protocol-defined dose in a day and experiences a drugrelated AE, this will be reported as an overdose and a protocol deviation. However, if the participant did not experience any AEs, this will only be reported as a protocol deviation.

The Investigator will discuss the risks and concerns of investigational agent exposure with the participant. Parents, guardians or participants are to be instructed to contact their study site immediately if an overdose of study drug is suspected. An overdose with AEs must be followed until the adverse effects are resolved or stabilized, or until reasonable attempts to determine resolution of the event are exhausted.

In the event of an overdose, the Investigator or treating physician should:

Contact the study Medical Monitor within 24 hours.

- Closely monitor the participant for any AEs/SAEs and laboratory abnormalities as medically appropriate and follow up until resolution, stabilization, the event is otherwise explained, or the participant is lost to follow-up.
- Document the quantity of the excess dose as well as the duration of the overdose in the eCRF.
- Report to Sponsor Safety only when associated with an SAE.

7.3. Environmental Exposure, Exposure During Pregnancy or Breastfeeding, and Occupational Exposure

Environmental exposure occurs when a person not enrolled in the study as a participant receives unplanned direct contact with or exposure to voxelotor. Such exposure may or may not lead to the occurrence of an AE or SAE. Persons at risk for environmental exposure include healthcare providers, family members, and others who may be exposed. An environmental exposure may include exposure during pregnancy (EDP), exposure during breastfeeding (EDB), and occupational exposure.

Any such exposures to voxelotor under study are reportable to Pfizer Safety within 24 hours of Investigator awareness.

7.3.1. Exposure During Pregnancy

An EDP occurs if:

- A female participant is found to be pregnant while receiving or after discontinuing voxelotor.
- A male participant who is receiving or has discontinued voxelotor inseminates a female partner.
- A female nonparticipant is found to be pregnant while being exposed or having been exposed to voxelotor because of environmental exposure. Below are examples of environmental EDP:
 - A female family member of healthcare provider reports that she is pregnant after having been exposed to voxelotor by all possible routes of exposure, eg, ingestion, inhalation, or skin contact.
 - A male family member or healthcare provider who has been exposed to voxelotor by all possible routes of exposure, eg, ingestion, inhalation, or skin contact, then inseminates his female partner prior to or around the time of conception.

The Investigator must report EDP to Pfizer Safety within 24 hours of the Investigator's awareness, irrespective of whether an SAE has occurred. The initial information submitted should include the anticipated date of delivery (see below of information related to termination of pregnancy).

- If EDP occurs in a participant/participant's partner, the Investigator must report
 this information to Pfizer Safety via PSSA regardless of whether an SAE has
 occurred. Details of the pregnancy will be collected after the start of voxelotor
 and until at least 140 days after the last dose.
- If EDP occurs in the setting of environmental exposure, the Investigator must report information to Pfizer Safety via PSSA. Since the exposure information does not pertain to the participant enrolled in the study, the information is not recorded on a CRF; however, a copy of the completed report is maintained in the Investigator site file.

Follow-up is conducted to obtain general information on the pregnancy and its outcome for all EDP reports with an unknown outcome. The Investigator will follow the pregnancy until completion (or until pregnancy termination) and notify Pfizer Safety of the outcome as a follow-up to the initial report. In the case of a live birth, the structural integrity of the neonate can be assessed at the time of birth. The child born to a female participant or partner of a male participant exposed to study drug will be followed for 3 months after delivery. In the event of a termination, the reason(s) for termination should be specified and, if clinically possible, the structural integrity of the terminated fetus should be assessed by gross visual inspection (unless pre-procedure test findings are conclusive for a congenital anomaly and the findings are reported).

Abnormal pregnancy outcomes are considered SAEs. If the outcome of the pregnancy meets the criteria for an SAE (ie, ectopic pregnancy, spontaneous abortion, intrauterine fetal demise, neonatal death, or congenital anomaly in a live born baby, a terminated fetus, an intrauterine fetal demise, or a neonatal death), the Investigator should follow the procedures for reporting SAEs. Additional information about pregnancy outcomes that are reported to Pfizer Safety as SAEs follows:

- Spontaneous abortion including miscarriage and missed abortion should be reported as an SAE;
- Neonatal deaths that occur within 1 month of birth should be reported, without regard to causality, as SAEs. In addition, infant deaths after 1 month should be reported as SAEs when the Investigator assesses the infant death as related or possibly related to exposure to voxelotor.

Additional information regarding the EDP may be requested by the Sponsor. Further followup of birth outcomes will be handled on a case-by-case basis (eg, follow-up on preterm infants to identify developmental delays). In the case of paternal exposure, the Investigator will provide the participant with the Parental Partner: Information Sheet and Informed Consent Form to deliver to his partner. The Investigator must document in the source documents that the participant was given the Pregnant Partner Release of Information Form to provide to his partner.

7.3.2. Exposure During Breastfeeding

An EDB occurs if:

- A female participant is found to be breastfeeding while receiving or after discontinuing voxelotor.
- A female nonparticipant is found to be breastfeeding while being exposed or having been
 exposed to voxelotor (ie, environmental exposure). An example of environmental EDB is a
 female family member or healthcare provider who reports that she is breastfeeding after
 having been exposed to voxelotor by all possible routes of exposure, eg, ingestion,
 inhalation, or skin contact.

The Investigator must report EDB to Pfizer Safety within 24 hours of the Investigator's awareness, irrespective of whether an SAE has occurred. The information must be reported using the PSSA. When EDB occurs in the setting of environmental exposure, the exposure information does not pertain to the participant enrolled in the study, so the information is not recorded on a CRF. However, a copy of the completed report is maintained in the Investigator site file.

An EDB report is not created when a Pfizer drug specifically approved for use in breastfeeding women (eg, vitamins) is administered in accordance with authorized use. However, if the infant experiences an SAE associated with such a drug, the SAE is reported together with the EDB.

7.3.3. Occupational Exposure

The Investigator must report any instance of occupational exposure to Pfizer Safety within 24 hours of the Investigator's awareness via PSSA regardless of whether there is an associated SAE. Since the information about the occupational exposure does not pertain to a participant enrolled in the study, the information is not recorded on a CRF; however, a copy of the completed report is maintained in the Investigator site file.

7.4. Lack Of Efficacy

The investigator must report signs, symptoms, and/or clinical sequelae resulting from lack of efficacy. Lack of efficacy or failure of expected pharmacological action is reportable to Pfizer Safety only if associated with an SAE.

7.5. Medication Errors

Medication errors may result from the administration or consumption of voxelotor by the wrong participant, or at the wrong time, or at the wrong dosage strength.

Medication errors are recorded and reported as follows:

Table 8. Reporting of Medication Errors

Recorded on the Medication Page of the CRF	Recorded on the Adverse Event Page of the CRF	Reported via PSSA to Pfizer Safety Within 24 Hours of Awareness
All (regardless of whether		Only if associated with an SAE
associated with an AE)	with the medication error	

Abbreviations: AE, adverse event; CRF, case report form; SAE, serious adverse event; PSSA: Pfizer's Serious AE Submission Assistant

Medication errors include:

- Medication errors involving participant exposure to the study drug
- Potential medication errors or uses outside of what is foreseen in the protocol that do or do not involve the study participant;
- The administration of an incorrect dosage;
- The administration of expired study drug;
- The administration of an incorrect study drug;
- The administration of study drug that has undergone temperature excursion from the specified storage range unless it is determined by the Sponsor that the study drug under question is acceptable to use.

Whether or not the medication error is accompanied by an AE, as determined by the Investigator, such medication errors occurring to a study participant are recorded on the medication error page of the CRF, which is a specific version of the AE page and, if applicable, any associated serious and nonserious AE(s) are recorded on the AE page of the CRF.

In the event of a medication dosing error, the Sponsor should be notified within 24 hours.

Medication errors should be reported to Pfizer Safety within 24 hours using PSSA only when associated with an SAE.

7.6. Data and Safety Monitoring Board

Not applicable to this open label trial.

8. BIOSTATISTICS

8.1. Statistical Methods

Statistical programming and analyses will be performed using established statistical methods. Details of all planned analyses will be specified in a separate statistical analysis plan (SAP).

The study data will be reported using summary tables, figures, and data listings. Continuous variables will be summarized using mean, standard deviation (SD), median, minimum, and maximum. Categorical variables will be summarized by presenting the number (frequency) and percentage in each category.

8.1.1. Study Endpoints

8.1.1.1. Safety

Safety data analysis will be performed on all participants enrolled in the study.

A treatment-emergent adverse event (TEAE) is defined as an AE that emerges on or after initiation of study drug (having been absent pretreatment), or an AE that existed pretreatment and worsened on treatment (relative to the pretreatment state). The incidence of TEAEs will be tabulated by system organ class (SOC), preferred term, severity and relationship to study drug. AEs considered to be related by the Investigator will be summarized. AEs will be reported by severity and relatedness to study treatment and classified via the Medical Dictionary for Regulatory Activities (MedDRA).

Changes in clinical laboratory data (hematology, serum chemistry, will be summarized.

For the laboratory safety data, out of range values will be flagged in the data listings and a list of clinically significantly abnormal values will be presented.

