5. TREATMENT OF SUBJECTS

Participants who complete 72 weeks of treatment on GBT440-031, regardless of a dose selection for GBT440-031, will receive voxelotor at the highest dose (either 900 or 1500-mg) deemed safe for continued assessment on the GBT440-031 study by the Data Safety Monitoring Board (DSMB).

Once a dose is selected for study GBT440-031, all GBT440-031 participants on the nonselected dose will be eligible to enroll into this OLE study at the selected dose. All participants already enrolled in this OLE study at the time of the dose selection will be administered the selected dose at their next scheduled assessment.

Participants may be eligible to enroll in this OLE study prior to GBT440-031 study completion based on interim data results and/or subsequent study modifications on GBT440-031. If this occurs, sites will be notified which participants are eligible.

When study GBT440-031 has completed, participants will be eligible to enroll in this study.

If a participant was on a reduced dose of voxelotor due to an AE in GBT440-031 or on this study prior to a dose selection on GBT440-031, dosing in this study may be continued at the reduced dose if deemed clinically appropriate by the Investigator. The original dose may be resumed if deemed clinically appropriate by the Investigator.

Participants may receive study drug as long as they continue to receive clinical benefit which outweighs risk as determined by the Investigator and/or until the participant has access to voxelotor from an alternative source (i.e., commercialization or through a managed access program).

The EOS visit can occur any time after participants obtains commercial voxelotor for participants who complete study per protocol. Participants should remain on study drug until EOS visit is completed.

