# 2.1. Study Design

Study GBT440-034 is a multicenter, global, open-label extension (OLE) study available to participants who were previously enrolled and treated in Study GBT440-031. Participants must meet the entry criteria for this study to be eligible for enrollment.

All participants enrolled in GBT440-034, regardless of treatment received in the parent study GBT440-031 (i.e., placebo, voxelotor 900 mg, or voxelotor 1500 mg), receive treatment with voxelotor 1500 mg once daily (the highest dose deemed safe for continued assessment based on GBT440-031).

All participants in Study GBT440-034 have scheduled study visits with assessments at Day 1, Week 12, Week 24, and Week 48, and then every 24 weeks thereafter. Participants who were treated with placebo or voxelotor 900 mg in Study GBT440-031 have additional study visits with assessments at Week 4 and Week 8.

Participants may receive voxelotor in GBT440-034 as long as they continue to receive clinical benefit which outweighs risk as determined by the Investigator and/or until the participant has access to voxelotor from an alternative source (i.e., commercialization or through a managed access program).

Additional details and background information are provided in the study protocol.

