#### 3.2. Visit Windows

For summaries by timepoint (e.g., laboratory values and vital signs), analysis visit windows will be used to classify assessments based on the actual treatment day of the measurement regardless of the original nominal visit label. This includes assessments collected at Unscheduled or EOS visits. Target study days, the protocol-specified study day windows, and the analysis visit windows are shown in Table 1.

**Table 1:** Analysis Windows

Timepoint	Target Study Day (relative to first dose)	Visit Window per Protocol (treatment days)	Window for Statistical Analysis (treatment days)
Baseline	1		Last value a taken on or prior to date of first dose in GBT440-034
Week 4	28	[23, 33]	[2, 42]
Week 8	56	[51, 61]	[43, 70]

Timepoint	Target Study Day (relative to first dose)	Visit Window per Protocol (treatment days)	Window for Statistical Analysis (treatment days)		
Week 12	84	[79, 89]	[71, 126]		
Week 24	168	[158, 178]	[127, 252]		
Week 48	336	[326, 346]	[253, 420]		
Week 72	504	[494, 514]	[421, 588]		
Week 96	672	[662, 682]	[589, 756]		
Week 120	840	[830, 850]	[757, 924]		
Week 144	1008	[998, 1018]	[925, 1092]		
Week 168	1176	[1166, 1186]	[1093, 1260]		
Week 192	1344	[1334, 1354]	[1261, 1428]		
	< Continues with 24-week intervals >				

Note: If multiple measurements fall within the statistical analysis window, the average of the measurements will be used.

Note that per the protocol Schedule of Assessments, laboratory assessments and vital signs are collected at visits up to Week 48. After Week 48, laboratory assessments are collected per standard of care for clinical management with the following exception: for participants enrolled outside of the US and Europe, hemoglobin and clinical measures of hemolysis (% reticulocytes, absolute reticulocytes, and bilirubin [total, direct, and indirect]) are collected after Week 48 at 24-week intervals (see Section 5.4.3).

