# **4.2.** Safety Population

The safety population includes all enrolled participants who received treatment with study drug (voxelotor) during Study GBT440-034.

The safety population will be the primary analysis population for this study.

Analyses will be presented for overall population, and by prior treatment group (i.e., placebo, voxelotor 900 mg, and voxelotor 1500 mg) based on treatment received in the parent study GBT440-031, as appropriate.

<sup>a Including Week 72, End of Treatment, or End of Study laboratory values collected in Study GBT440-031.

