#### **5.3.2.** Adverse Events

Adverse events will be classified according to MedDRA; the most current version at the time of analysis will be used. Severity of adverse events will be graded using the National Cancer Institute Common Terminology Criteria for Adverse Events (NCI CTCAE) version 4.03, when possible, or based on the protocol-specified grading for adverse events not covered in the NCI CTCAE.

Non-SCD-related adverse events and SCD-related adverse events will be summarized separately. SCD-related adverse events include sickle cell anaemia with crisis, acute chest syndrome, pneumonia, priapism, and osteonecrosis. All other adverse events will be considered non-SCD-related.

Summaries of TEAEs, defined as adverse events with an onset on or after the date of informed consent until 28 days after last dose of study drug, will be tabulated by MedDRA system organ class (SOC) and preferred term, as appropriate.

Summaries of TEAEs will be provided for the following categories:

- Non-SCD-related TEAEs
- Non-SCD-related TEAEs by study year
- Non-SCD-related TEAEs by maximum severity
- Non-SCD-related TEAEs assessed as related to study drug by the investigator
- Non-SCD-related TEAEs of rash (group term)
- Non-SCD-related TEAE of abdominal pain (group term)
- Non-SCD-related treatment-emergent serious adverse events (SAEs)
- Non-SCD-related treatment-emergent SAEs by study year
- Non-SCD-related treatment-emergent SAEs assessed as related to study drug by the investigator
- SCD-related TEAEs
- SCD-related TEAEs by study year
- SCD-related TEAEs by maximum severity
- SCD-related TEAEs assessed as related to study drug by the investigator

- SCD-related treatment-emergent SAEs
- SCD-related treatment-emergent SAEs by study year
- SCD-related treatment-emergent SAEs assessed as related to study drug by the investigator
- All TEAEs leading to study drug discontinuation
- All TEAEs leading to study drug dose modification (dose reduction or interruption)

Listings for all adverse events, adverse events leading to study drug discontinuation, SAEs, and deaths will be provided.

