## **5.4. SCD-Related Complications**

## 5.4.1. Frequency of SCD-Related Complications

SCD-related complications include adverse events of acute chest syndrome, hepatic sequestration, leg ulcers, osteonecrosis, pneumonia, priapism, pulmonary hypertension, retinopathy, scleral icterus, sickle cell anaemia with crisis, splenic sequestration, and stroke.

The incidence and the annualized incidence rate of each SCD-related complication based on TEAEs, as well as the total of all SCD-related complications, will be computed. Annualized incidence rates will be estimated by dividing the total number of complications observed for all participants by the total assessment time for all participants, and 95% confidence intervals provided based on exact Poisson confidence limits.

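### The whole-study adverse event tables in SAP 5.3.2 carry no person-time measure although follow-up is open-ended, and the by-study-year tables that partly make up for this state no denominator

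*Protocol*

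**What the plan says.** **How events are summarized.** Protocol 8.1.1.1: "The incidence of TEAEs will be tabulated by system organ class (SOC), preferred term, severity and relationship to study drug". Protocol 8.1 sets the general rule: "Categorical variables will be summarized by presenting the number (frequency) and percentage in each category". SAP 5.3.2, which takes precedence where the two differ (SAP 2), says that TEAE summaries "will be tabulated by MedDRA system organ class (SOC) and preferred term, as appropriate". It lists tables of non-SCD and SCD-related TEAEs and SAEs, by maximum severity and by relatedness, and of all TEAEs leading to discontinuation or dose modification. No time denominator is named for any of them.

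**How long participants are followed.** Protocol 5: "Participants may receive study drug as long as they continue to receive clinical benefit which outweighs risk as determined by the Investigator". The other stopping point, in SAP 2.1, is "until the participant has access to voxelotor from an alternative source". SAP Table 1 lists windows to Week 192 and then adds "< Continues with 24-week intervals >".

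**How results are shown.** SAP 4.2: "Analyses will be presented for overall population, and by prior treatment group". The rest of that sentence defines the groups by parent-study treatment and limits this to where it is appropriate.

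**What already allows for time.** SAP 5.3.2 also plans TEAEs and SAEs by study year, for non-SCD and SCD-related events. For SCD-related complications, SAP 5.4.1 says: "Annualized incidence rates will be estimated by dividing the total number of complications observed for all participants by the total assessment time", with exact Poisson 95% confidence limits. Time on study (SAP 5.2) and duration of exposure (SAP 5.3.1) are summarized, but neither is used as a denominator for adverse events.

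**The concern.** The study exists to describe safety over long use, yet its main safety tables give the share of participants who ever had an event over observation periods of very different length. One participant may leave after a few months for commercial supply and another may stay four years. Both count once in the denominator. The resulting percentage mixes risk with time observed.

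Two things are at stake. The overall percentage for an event has no clear meaning unless the reader knows the time behind it. And if the prior placebo, 900 mg and 1500 mg groups were observed for different lengths of time, equal risk would show as unequal percentages, or a real difference could be masked.

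The by-study-year tables are the natural safeguard, but SAP 3.1 defines only how an event is assigned to a year. It does not say whether the percentage for Year 3 is taken over everyone treated or over those still observed in Year 3. There is also no by-year table for related events, maximum severity, discontinuation or dose modification.

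**Working it through.** The documents give no event rate and no follow-up by group, so there is no planned figure to reproduce. All rates and leaving patterns below are assumptions chosen to show the mechanism.

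**1. Percentage against time at constant risk.** Input from SAP Table 1: Week 192 is day 1344, so 1344/365.25 = 3.68 years. Likewise 48 weeks = 336/365.25 = 0.92 years and 144 weeks = 1008/365.25 = 2.76 years. Formula: crude % = 100 × (1 − exp(−rate × years)).

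| Assumed first-event rate per year | 48 weeks | 144 weeks | 192 weeks |
|---|---|---|---|
| 0.02 | 1.8% | 5.4% | 7.1% |
| 0.05 | 4.5% | 12.9% | 16.8% |
| 0.10 | 8.8% | 24.1% | 30.8% |
| 0.30 | 24.1% | 56.3% | 66.8% |

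For the 0.10 row: 1 − exp(−0.092) = 8.8% and 1 − exp(−0.368) = 30.8%. In every column the exposure-adjusted rate is the assumed rate.

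**2. Two groups with the same risk (0.10 per year) and different follow-up.**

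| Follow-up, weeks | Crude % | Apparent difference |
|---|---|---|
| 132 v 144 | 22.4 v 24.1 | 1.8 points (before rounding) |
| 120 v 144 | 20.5 v 24.1 | 3.6 points |
| 96 v 144 | 16.8 v 24.1 | 7.3 points |

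The artefact is small when follow-up is similar and material when it is not.

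**3. By-year tables: the denominator matters.** Assume 0.10 events per year and 25% leaving each year, so the leaving hazard is −ln(0.75) = 0.288. The chance of an event in a year, among those who start it, is 0.10/(0.10 + 0.288) × (1 − exp(−0.388)) = 8.3%. Dividing instead by all treated multiplies this by 0.75 for each earlier year.

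| Denominator | Year 1 | Year 2 | Year 3 | Year 4 |
|---|---|---|---|---|
| Under observation at start of year | 8.3% | 8.3% | 8.3% | 8.3% |
| All treated | 8.3% | 6.2% | 4.7% | 3.5% |

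The second row shows a decline that is due only to participants leaving.

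**4. Is a rate alone enough?** Assume the same risk in both groups, 0.60 per year for the first half-year and 0.10 after it, with exponential follow-up of mean m years. Put a = 0.60 + 1/m, b = 0.10 + 1/m and S = exp(−0.5a). Expected first events per participant are (0.60/a)(1 − S) + S(0.10/b). Expected time at risk is (1 − S)/a + S/b.

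- m = 2.0: S = 0.577, events 0.327, time 1.346 years, rate 24.3 per 100 person-years.
- m = 2.8: S = 0.620, events 0.374, time 1.753 years, rate 21.3 per 100 person-years.

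With identical risk, the crude percentages (32.7 v 37.4) and the rates (24.3 v 21.3) both differ, in opposite directions. The rate removes the artefact only when the hazard is roughly constant.

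**The case against.** The strongest case against is that the plan already deals with time in several places. All five terms that SAP 5.3.2 classes as SCD-related are in the SAP 5.4.1 list and get annualized rates. TEAEs and SAEs are tabulated by study year, and Year 1 is where an excess at the start of treatment would show. Exposure and time on study are reported. Everything is descriptive, with no tests. Table layouts sit in a separate mock-up document (SAP 6), which may already contain the missing column. And a single rate has its own artefact, as step 4 shows.

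Most of this stands, and it limits the point. A reader might infer that all TEAE reporting ignores time. SAP 5.4.1 shows otherwise, so the gap lies mainly in non-SCD events, SAEs, related events, discontinuations and dose modifications. A reader might also infer that general TEAE percentages will be set against the 72-week parent study. Protocol 8.1.1.2 and 8.1.1.2.1 plan a parent-study comparison only for SCD complications, transfusion and opioid use. For general TEAEs it would be a misreading, not a planned analysis.

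The objection does not remove the gap. The by-year tables leave out related events, maximum severity, discontinuations and dose modifications, and have no stated denominator. A separate exposure summary does not let a reader turn a percentage into a first-event rate. What the mock-ups contain cannot be checked here, and the rule belongs in the SAP text.

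**Conclusion.** The point holds as a cheap improvement. For the tables named, the SAP gives no person-time measure over follow-up that is open-ended and varies between participants, so the percentages partly measure time observed. The size depends on the event rate: at an assumed 10 per 100 person-years, 8.8% at 48 weeks becomes 30.8% at 192 weeks with no change in risk.

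It is tempting to go further and say that the prior-treatment groups do differ in follow-up, so that their percentages are biased against one another. The documents do not support that. All groups share one stopping rule, and no follow-up by group is given. Protocol 3.1.2 lets participants on the non-selected dose enter before 72 weeks, so a difference is possible, but its direction is not known. The supportable statement is conditional: the percentages cannot be safely compared between groups if follow-up differs. The 1.8 to 7.3 point differences in step 2 are illustrations under assumed follow-up, not estimates for this trial. Nor do the documents rank safety as a primary objective; SAP 2 and Protocol 2 state one objective covering safety and treatment effect.

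**What to change.** In SAP 5.3.2:

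1. For the whole-study tables of non-SCD TEAEs, SAEs, related events, and TEAEs leading to discontinuation or dose modification, add beside n (%) the exposure-adjusted incidence rate: participants with at least one event per 100 person-years. Time runs from the start of the TEAE window (informed consent) to the first event or, without one, to the earlier of last dose + 28 days and End of Study. The second limit matters because completers may have their End of Study visit while still on drug. Show person-years and a 95% CI, overall and by prior treatment group.
2. For the by-study-year tables, state that the denominator is participants still under observation at the start of that year.
3. State that any contrast between prior-treatment groups is read from the rates together with the by-year tables, not from whole-study percentages or from the rates alone.

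The cost is SAP wording and one extra column, from dates already collected. The downside is that a single rate averages over a changing hazard and can itself mislead when risk is front-loaded and follow-up differs, which is why item 3 ties it to the by-year tables.
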